#### **CLINICAL TRIAL MASTER PROTOCOL AND INVESTIGATIONAL BROCHURE INFORMATION \***

	Master Protocol	Investigator Brochure: <specify Drug/Device></specify 	Investigator Brochure: <specify Drug/Device></specify 	Sponsor Consent Form Template(s)
Version #:				
Version Date:				

**[ x ]** This study is investigator-authored (investigator developed the study and is conducting the study at UCI and/or with other non-UCI sites).

\* Add columns as applicable

#### NON-TECHNICAL SUMMARY

Provide a brief non-technical summary or synopsis of the study that can be understood by IRB members with varied research backgrounds, including non-scientists and non-affiliated members.

Vitiligo is a dermatologic disease characterized by depigmentation of skin. While the loss of melanocytes observed in vitiligo is driven by the immune system, repigmentation of the skin that occurs during UV light treatment is driven by melanocytes that migrate out of the hair follicle and into epidermis or the activation of stem cells within the epidermis. Unfortunately, some skin areas affected by vitiligo have very few hair follicle melanocytes and an indeterminate number of epidermal melanocytes and therefore unable to respond to light therapy.

This pilot study seeks to establish a relatively new procedure- the melanocyte keratinocyte transplant procedure (MKTP)- at UC Irvine Healthcare as a method to treat depigmented skin in vitiligo patients.

In addition, this study will utilize single cell RNA sequencing technology to identify the different population of melanocytes in cells harvested for the transplant procedure in an effort to identify the specific type of melanocyte that is responsible for vitiligo repigmentation.

Patients in [name] clinic at UCI Department of Dermatology will approach for participation in the study. The study will include both men and women and will not be limited by race or ethnicity. We will exclude less than 18 years old for the study as we believe it would be difficult for these subjects to tolerate the melanocyte keratinocyte transplant procedure. Patients offered a melanocyte keratinocyte transplant procedure. Patients offered a melanocyte keratinocyte transplant procedure. This procedure is a method to transplant a large area of skin with a suspension of melanocytes and keratinocytes that is generated from 1-3/10th the surface area of epidermis. This study has three arms:

- 1- MKTP with Surgical Blade
- 2- MKTP with Negative Pressure Instrument (suction blistering device).
- 3- Suction blister grafting without cell dissociation

On the first arm of the study, A normally pigmented area on the patient was anesthetized with 1% lidocaine with epinephrine. Using a surgical knife, we removed a small portion of the epidermis that is unaffected by vitiligo from a small area (2cm^2) on the patient's thigh to obtain donor cells. Epidermis that was harvested with the surgical knife was washed with Lactated Ringers solution three times, and then dissociated using trypsin to separate the cells into a single cell suspension. The recipient area to be grafted was ablated with an Erbium YAG laser. Half of the dissociated single cells from the donor area (thigh)was then transplanted on to the area affected by vitiligo that the patient is interested in grafting (5 cm^2 area).

We then evaluated response to treatment in the transplanted areas at 1 day, 1 week, 1 month and 3 months, and 6 months by both photography and quantifying the VASI score.

VASI is the percentage of vitiligo involvement and is calculated in terms of hand units. One hand unit is approximately equivalent to 1% of the total body surface area.

On the second arm of the study, we are using a minimally invasive procedure (suction blister grafting) to sample the grafted skin and donor skin- this method can separate the epidermis from the dermis without inducing a scar. A normally pigmented area on the upper thigh is anesthetized with 1% lidocaine with epinephrine. Using a suction blister technique, we remove a small portion of the epidermis that is unaffected by vitiligo from a small area (4 cm^2 or 0.6 inch) on the patient's thigh to obtain donor cells. Epidermis that was harvested is washed with Lactated Ringers solution three times, and then dissociated using trypsin to separate the cells into a single cell suspension. The recipient areas to be grafted is used to harvest epidermis using a suction blister device. Half of the dissociated single cells from the donor area (thigh) are then transplanted on to the area affected by vitiligo that the patient was interested in grafting (5 cm^2 area or 0.7 inch). The suction blister skin from the recipient sites is simultaneously dissociated into a single cell suspension. A portion of the remainder of the cells (from both the donor and recipient site) is subjected to flow sorting to quantify the populations of melanocytes and keratinocytes. Another portion of the remainder cells are submitted for single cell RNA-sequencing at the genomics and high throughput facility to identify the spectrum of different types of melanocytes and keratinocytes in the epidermis using single cell RNA-sequencing technology. We then evaluated response to treatment in the transplanted areas at 1 day, 1 week, 1 month and 3 months, and 6 months by both photography and quantifying the VASI score. This arm of the study is nearly complete, with only 2-3 more patients to enroll to complete the statistical evaluation of efficacy.

VASI is the percentage of vitiligo involvement and is calculated in terms of hand units. One hand unit is approximately equivalent to 1% of the total body surface area.

On the now proposed third arm of the study, we use a minimally invasive procedure (suction blister grafting without cell dissociation) to sample the grafted skin and donor skin- this method can separate the epidermis from the dermis without inducing a scar. A normally pigmented area on the upper thigh will be anesthetized with 1% lidocaine with epinephrine. Using an epidermal harvesting system which is a suction blister technique, we will remove multiple small portions (about 128 blisters-1.8 mm in diameter) of the epidermis unaffected by vitiligo from a small normal area (5 cm^2) on the patient's thigh to obtain donor cells and using a regular negative pressure instrument for removing four samples for histopathological study (two from the vitiligo area and two from the normal donor skin). The epidermis from the donor area (thigh) will then be transplanted on to the area affected by vitiligo that the patient is interested in grafting. Also, the four portions from the normal skin and the recipient site will be sent for the histopathological evaluation.

We will then evaluate response to treatment in the transplanted areas at 1 day, 1 week, 1 month and 3 months, and 6 months by both photography, quantifying the change in depigmented surface area, and the VASI score. Also, we will evaluate the two vitiligo samples and two normal skin samples through histopathology to assess where the unique populations of cells identified in our RNA-seq analysis are localized. We hypothesize that our transplant procedure will yield excellent to good repigmentation, resulting in a mean of 60% reduction in surface area (SD=30%) from baseline to 6-month follow up. With a sample size of 5 patients, this study will achieve 90% power to test this hypothesis based on a two-sided paired t-test at p=0.05 significance level. In addition, we will compare the results from the 7 patients harvested using the surgical blade technique (procedure already completed and follow up results pending) with the results from 7 patients harvested with the suction blisters (almost completed) and seven patients from the newly proposed experimental group.

### SECTION 1: PURPOSE AND BACKGROUND OF THE RESEARCH

1. Provide the scientific or scholarly rationale for the research. Describe the relevant background information and the specific gaps in current knowledge that this study intends to address.

Vitiligo is a dermatologic disorder characterized by depigmented areas of skin caused by immunemediated melanocyte destruction. This disease has an estimated prevalence of 0.5-4 percent worldwide; however, the prevalence can reach as high as 8% in certain parts of the world. The visual appearance of vitiligo can have serious social, mental and emotional impact on patients with this disease, leading to a poor quality of life and increased incidence of depression and suicide. In addition, the disease has many unique biologic aspects that make it very interesting to study. While the process is initiated by the immune system, repigmentation is driven by melanocyte stem cells that migrate to and repigment the epidermis. This is not a static process but a dynamic one—areas of skin are constantly losing pigment and new melanocytes are migrating to repigment the area. It is not known why this depigmentation initiates only in certain areas, or how the repigmentation occurs. Nothing is known about how many melanocyte populations there are in the skin, and which one of these contribute to repigmentation. Answering this basic question will not only give insight into the disease and its treatment, but also elucidate mechanisms that underlie epithelial regeneration itself. There are limited treatments for vitiligo and no known cure. The gold standard for treatment of vitiligo is narrow band UVB light therapy, which induces follicular epidermal melanocytes to migrate to the epidermis. This is not a uniformly successful treatment and requires often greater than 50 treatments for an adequate therapeutic response, which takes up to three months to see. Unfortunately, this treatment does not work if the affected skin lacks a melanocyte stem cell reservoir, such as occurs in segmental vitiligo.

Standard surgical management of vitiligo involves transplanting normal melanocytes into depigmented areas. While the UCI Dermatology Clinic currently performed punch grafting transplantation procedures, recent advances have established the melanocyte-keratinocyte transplant procedure (MKTP) as a more effective way to treat the disease. The procedure involves harvesting a small area of epidermis from normal skin (usually the thigh), destroying the epidermis in an affected area of skin, and transplanting the single cell epidermal suspension onto the affected area. This method has the advantage of harvesting only small pieces of skin to treat large affected areas (can treat an area 10x as large as the donor site). It has a 70% success rate as documented by recent studies after specialized training. [name], the PI on the study, completed a course to learn the procedure at Henry Ford Hospital, the first site that performed this procedure in the United States. The procedure is currently performed at UT Southwestern, U Mass Amherst, and Henry Ford Hospital. Upon completion of this pilot study to collect preliminary outcome data on the procedure at UCI, UC Irvine will become the first institution on the west coast to offer the treatment to patients. In a desire to continuously innovate and develop an even better procedure, we are harvesting skin from the donor site and skin from the recipient site using a surgical blade in the first arm of the study, blister grafting technique with dissociation of the cells in the second arm of the study and transplanting the blisters without dissociation of the cells in the third arm of the study. Suction blistering method is a more uniform way to remove the epidermis without inducing a scar, making it safer than the original published MKTP technique. One of the issues with current grafting methods is the need for specialized equipment for cell dissociation, which can often be tedious and time consuming. We ask the question whether this dissociation really results in a better outcome in the third arm of the study. In the third arm of the study, we will use Cellutome suction blister grafting without cell dissociation. With Cellutome, we can harvest more grafts in a shorter time. As each blister is smaller in size, there is a smaller risk of scarring after the procedure.

Blister grafting without cell dissociation has been tested by many researchers in the past with good results .

In a study by Budania et al, suction blister epidermal grafting was compared with autologous noncultured epidermal cell suspension. Most of the subjects in this study showed >75% repigmentation. In another study by Li J et al, suction blister epidermal grafting was performed for one thousand one hundred subjects with stable vitiligo . Excellent repigmentation was observed in > 80% of the patients . Babu et al conducted a comparison study between punch grafting and suction blister epidermal grafting in the treatment of stable lip vitiligo . In this study, more than half of the patients in both groups showed more than 50 % repigmentation .

Cellutome epidermal harvesting system can harvest more grafts in a shorter time in comparison to the Negative Pressure Instrument which makes the transplantation easier, faster and more efficient.

2. Provide relevant preliminary data (animal and/or human).

Melanocyte-Keratinocyte Transplant Procedure (MKTP) has been performed in many institutions in Europe, Asian and throughout the Middle East. It has also recently been established in the United States at Henry Ford Hospital Multicultural Dermatology Center. Recent publication of result following MKTP shows it to be an effective and well-tolerated treatment option for vitiligo. (5) Dellatorre et al demonstrated that Suction Blister Epidermal Graft is a low cost and effective option (65 to 100% repigmentation can be achieved in up to 80% of patients).

(6) In another study, Jeong H S et al proved that Non-cultured epidermal suspension grafting is a useful surgical intervention in patients with stable vitiligo, capable of promoting repigmentation in areas refractory to medical intervention and allowing a donor-to-recipient ratio of up to 1:10.

(7) In another study Ashique KT et al demonstrated that suction blister epidermal graft continues to be a good, cost-effective, surgical method of treating vitiligo especially on the face and lip. The donor site also tends to show good healing tendency with minimal scarring and post inflammatory pigmentation. (8) Also in another study by Gou D et al found that Blister grafting is successful in most patients with vitiligo, with a high graft survival rate (9). Also, Strassner JP et al demonstrated that suction blistering technic does not increase the risk of vitiligo on the blister areas. (10)

3. Describe the purpose, specific aims or objectives. Specify the hypotheses or research questions to be studied.

The purpose of this study is to compare the result of suction blister grafting without cell dissociation versus suction blister grafting with cell dissociation and MKTP with blade technique and determine whether cellular dissociation impacts the outcome. In the first arm of this study, seven patients were enrolled, and the procedure was done successfully without complication. Follow up was accomplished and outcomes will be analyzed at the end of the study. In the second arm of the study, we have conducted the MKTP with suction blistering in 7 patients and then will compare the results with previous study. In the third arm of the study, we are planning to perform suction blister grafting without epidermal cell dissociation on a total of seven patients. We want to evaluate the importance of cell dissociation on the outcome of this procedure.

This information and experience will be important worldwide for the vitiligo community, as it is the only study that compares the efficacy of these three methods in a single study. This will help us better advice and counsel patients on the best procedure for them when we discuss the options. UCI is the only center on the west coast offering this procedure, so ensuring the efficacy of the methods is important.

In addition, we want to use the unique opportunity of this three-arm pilot study to characterize the different melanocyte and keratinocyte populations that exist in the epidermis, populations that may be important in the pathogenesis of vitiligo itself. The MKTP procedure works to repigment vitiligo yet does not involve transplantation of hair follicle melanocyte stem cells, as only the epidermis is harvested during the procedure. To identify what this migrating population might be, we will first seek to identify the different populations of melanocytes that are present in the normal epidermis using single cell RNA-seq. In addition, we will perform RNA-seq on the affected skin to examine the contributions of keratinocytes to the pathogenesis of the disease. In the third arm, we will harvest tissue for spatial localization of the different cell types, which will really allow us to determine which cells are contributing to vitiligo pathogenesis. With the new modification, we are also adding in methods to sort the transplanted cells to both monitor the success of the procedure and develop methods to identify the right cells to transplant.

4. Describe the primary outcome variable(s), secondary outcome variables, and predictors and/or comparison groups as appropriate for the stated study objectives/specific aims.

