#### Study Endpoints:

We hypothesize that our transplant procedure will yield excellent to good repigmentation, resulting in a mean of 60% reduction in surface area and VASI scores (SD=30%) from baseline to 6-month follow up. With a sample size of 5 patients, this study will achieve 90% power to test this hypothesis based on a two-sided paired t-test at p=0.05 significance level. This will be measured by both the physician and captured via digital photography. In the second arm of the study, we will compare the results with skin harvested with a blade as compared to a suction blister method. In the third arm of the study, we will compare the results skin harvested with a blade as compared to a suction blister method as used to a suction blister with dissociation and suction blister without dissociation.

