#### I. Statistical Considerations (This section is required for Investigator-Authored Research)

1. Statistical Analysis Plan: Describe the statistical method(s) for the stated specific aims and hypotheses. Your analysis plans should match the stated study specific aims and hypotheses in Section 1.

[] Not applicable

This is an observational study to examine response to therapy using change in surface area and VES score. There will be no measurement other than improvement in surface area and VES score as a measure of improvement before and after the procedure.

2. Describe the primary statistical method(s) that will be used to analyze the primary outcome(s) or endpoints.

We will measure the VES score and surface area change in the transplanted area before and after the procedure. The rate of change in surface area and VES will be measured as an outcome measure. This study is powered to examine if the initial procedure induces significant repigmentation (10 patients for each arm) and is also sufficient to compare the initial procedure to the procedure with the blister grafting technique.

3. Describe the secondary statistical method(s) that will be used to analyze the secondary outcome(s) or endpoints.

N/A

4. If appropriate describe secondary or post hoc analyses of primary outcome(s) or other exploratory analysis.

N/A

5. Sample Size Determination: Explain how the overall target sample size was determined (e.g., power analysis; precision estimation), providing justification of the effect size for the primary outcome based on preliminary data, current knowledge/literature and/or cost consideration; if appropriate, provide sample size justification for secondary outcomes. Power analysis should (at least) match the primary outcome/endpoint.

With a sample size of 5 patients in each arm, this study will achieve 90% power to test the hypothesis for each arm based on a two-sided paired t-test at p=0.05 significance level.

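### No pair of arms isolates cell dissociation, so the dissociation part of the study purpose cannot be answered; the procedures can be compared only as complete packages

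*Combined protocol and SAP*

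**What the plan says.** Section 1, item 3 gives a purpose in two parts. The first is to compare the results of three techniques. The second is to "determine whether cellular dissociation impacts the outcome", repeated at the end of that paragraph as "We want to evaluate the importance of cell dissociation on the outcome of this procedure". The same item then draws a practical consequence: "This will help us better advice and counsel patients on the best procedure for them when we discuss the options".

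The dissociation question recurs in two places. The rationale (Section 1, item 1) says "We ask the question whether this dissociation really results in a better outcome in the third arm of the study". Study Endpoints (Section 6.B, item 2) ends its third-arm comparison with "suction blister with dissociation and suction blister without dissociation".

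Section 6.B, item 1 describes a longitudinal study against baseline. The form asks there for any randomisation or blinding scheme, and the answer gives none. Section 6.I, item 1 calls the study observational. Section 6.I gives no between-arm method or adjustment and answers N/A for secondary and exploratory methods. Item 2 nevertheless says the study "is also sufficient to compare the initial procedure to the procedure with the blister grafting technique". The only calculation anywhere is for a paired t-test within each arm.

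**The concern.** To say that dissociation affects outcome, the plan needs two groups that differ in dissociation and are otherwise alike, or a way to remove the other differences. If several steps change together, a difference between arms could come from any of them. A lack of difference could equally be two effects cancelling.

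A report that followed Section 1 as written would credit or discredit dissociation on evidence that cannot separate it from the device, the preparation of the bed or the calendar period. That reading would then feed into the patient counselling that Section 1 has in view.

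**Working it through.** **Step 1. The arms side by side** (Non-technical Summary; Section 6.C, item 1):

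| Feature | Arm 1 | Arm 2 | Arm 3 |
|---|---|---|---|
| Graft form | Dissociated | Dissociated | Not dissociated |
| Harvest tool | Skin-grafting knife | Regular suction device | Cellutome |
| Recipient bed | Erbium-YAG laser | Suction blisters | Erbium-YAG laser |
| Share of harvest grafted | Half the cells | Half the cells | Harvested epidermis, no split stated |
| Stated donor area | 2 cm² | 4 cm² | 5 cm² |
| Stated recipient area | 5 cm² (Summary), 5–10 cm² (6.C) | 5 cm² | 5–10 cm² |
| Period | Procedures finished | Nearly complete, or 7 done | Proposed |

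Two entries rest on text that is not consistent. For arm 1, the rationale in Section 1, item 1 refers to "skin from the recipient site using a surgical blade in the first arm of the study", whereas the Summary and Section 6.C describe a laser at the recipient site. For arm 2, the Summary says 2–3 patients are still to be enrolled. Against the target of 7 in Section 3.A, that means 7 − 3 = 4 to 7 − 2 = 5 patients treated. Section 1, item 3 says "we have conducted the MKTP with suction blistering in 7 patients". Neither conflict changes the conclusion.

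**Step 2. Each pair in turn.**
- Arm 1 v 2: both dissociated, so the pair carries no information on dissociation.
- Arm 2 v 3: differs in dissociation, but also in bed preparation, harvest device, share grafted, stated donor area, stated recipient area and, largely, period.
- Arm 1 v 3: the laser bed is shared on the Section 6.C description, but harvest tool, share grafted, stated donor area and period differ.

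Pairs that isolate dissociation: 0 of 3.

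**Step 3. Could adjustment or a larger sample help?** Absence of dissociation, use of Cellutome and membership of arm 3 coincide in every patient. No contrast among these arms, and no regression on them, can separate the first two. More patients would narrow the interval around the same mixed quantity.

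**Step 4. What the stated power covers.** Inputs from Section 1, item 4 and Section 6.I, item 5: mean reduction 60%, SD 30%, n = 5, two-sided 0.05, paired t-test. The standardised effect is 60/30 = 2, the noncentrality 2 × √5 = 4.47, with 4 degrees of freedom. Power is 0.909, which reproduces the stated 90%. It concerns change from baseline within one arm and says nothing about a difference between arms.

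**Step 5. Between-arm precision.** The plan gives no between-arm difference or SD, so I assume that the SD of 30 points applies to the percentage reduction in each arm. The 95% half-width is t(0.975, 2n − 2) × SD × √(2/n).
- 7 v 7, SD 30: 2.179 × 30 × 0.5345 = 34.9 points.
- 7 v 7, SD 20: 23.3 points; SD 40: 46.6 points.
- 10 v 10 (the number named in Section 6.I, item 2), SD 30: 2.101 × 30 × 0.4472 = 28.2 points.

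With SD 30, a two-sample t-test at two-sided 0.05 reaches 80% power only for a true difference of about 49 points at 7 v 7, or 40 points at 10 v 10.

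**The case against.** The strongest reply is that this is a pilot, labelled observational and longitudinal against baseline, with no between-arm test specified. One site, one eligibility list and one follow-up schedule serve all three arms. Comparing complete procedures is a legitimate descriptive aim, and confounding does not forbid an estimate with a confidence interval. All of that stands, and it limits the point to the dissociation wording and the best-procedure reading. It does not rescue the dissociation wording, because Section 1 states a causal question that a modest design label does not answer.

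Four stronger readings are tempting but unsupported:
- *The whole purpose fails.* It does not. The comparison of three techniques can be reported as an exploratory comparison of packages, and the within-arm hypothesis is untouched.
- *Patient selection differed between arms.* Candidacy rests on the lead researcher's judgement (Section 3.C), so selection could drift across sequential arms, but no drift is documented.
- *The periods are wholly separate.* On the Summary's account, the last 2–3 arm 2 patients could overlap with arm 3.
- *The sufficiency statement in Section 6.I is a claim about dissociation.* It most naturally means arm 1 against the blister technique with dissociation. Its fault is separate: no calculation supports it.

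**Conclusion.** The dissociation part of the purpose, with its echoes in the rationale and Study Endpoints, cannot be met. The arm 2 v 3 contrast carries at least five stated technical or area differences besides dissociation, plus most of the calendar period. Arm 1 v 3 is better matched on the bed but still mixed with harvest tool, share grafted, donor area and period. This rests on the procedures as Section 6.C describes them and on the absence of any randomisation or adjustment in Sections 6.B and 6.I. It does not assume that the device or the bed method changes repigmentation; the documents do not say, and the design could not tell.

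The counselling sentence needs the same limit, since sequential, non-randomised arms do not show that one procedure is better. Imprecision is secondary. A half-width of about 35 points, under the carried-over SD of 30, is more than half of the 60-point reduction hypothesised within an arm (35/60 = 0.58).

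**What to change.** 1. **Section 1, item 3.** Replace the two dissociation sentences with: *exploratory comparison of three complete procedures (harvest + bed preparation + graft form) in sequential, non-randomised arms*. Qualify the counselling sentence to match.
2. **Section 1, item 1 and Section 6.B, item 2.** Keep the question in the rationale as motivation, adding that between-arm differences in this study cannot be attributed to dissociation alone. Align Study Endpoints.
3. **Section 6.B, item 1 and Section 6.I.** Add: *Arms are sequential and non-randomised; between-arm differences will be reported as estimates with 95% confidence intervals and will not be attributed to dissociation or any other single component.*
4. **Section 6.I, item 2.** Delete the sufficiency statement, or replace it with the expected precision of the between-arm estimate and the SD assumed.
5. **Optional.** List enrolment order, body site and donor and recipient area per patient beside the outcome, using coded data.

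The investigators should also reconcile the passages that disagree on technique, area and arm 2 enrolment; which is right is for them to say.

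The cost is wording in Sections 1 and 6, with no new patients or visits. The price is a narrower claim: the dissociation question stays open. Answering it would need concurrent arms that differ only in that step, which is a redesign and is not requested here.
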